8.5.2 Adverse Events

The number and percent of ALT-103-201 subjects with any TEAEs will be displayed by SOC and PT for each dose group. Within each PT, subjects will be counted only once if they had more than one event reported during the treatment period.

The number and percentage of subjects with any TEAE will be presented as well as the corresponding 95% Clopper-Pearson exact CI of the percentage.

For MedDRA SOC, the number and percentage of subjects experiencing at least one TEAE overall and at least one TEAE for a system will be tabulated by severity grade (Grades 1-4) and dose group. For MedDRA PT, the number and percentage of subjects reporting at least one TEAE within a PT category will be tabulated by relationship to study products and dose group. For the calculations in these tables, each subject's TEAEs will be counted once under the maximum severity or the strongest recorded causal relationship to study product.

Summaries will be generated for all serious TEAEs, TEAEs resulting in dose withdrawal, treatment emergent MAEs, and treatment emergent NCI, by SOC and PT for each dose group.

A listing will be produced for all subjects who reported serious TEAEs. The listing will provide details of the events including severity, relationship to study product, time between onset and last study treatment administration, and a summary of the event.

All TEAEs and non-treatment emergent AEs will be listed individually by subject.

8.5.3 Safety Laboratory Tests

Safety laboratory results for ALT-103-201 subjects will be summarized descriptively for each parameter with continuous values and dose group by visit for the observed value as well as for the change from baseline value. In addition, laboratory shift tables will be provided for all laboratory parameters where grades can be ascertained.

The following safety laboratory parameters will be collected for ALT-103-201 subjects:

- Hematology: hemoglobin, platelet count, white blood cell count with differential (absolute or percent counts of neutrophils, lymphocytes, monocytes, basophils, eosinophils)
- Serum chemistry: alkaline phosphatase, alanine aminotransferase (ALT), aspartate aminotransferase (AST), bicarbonate, bilirubin, chloride, creatine kinase, creatinine, glucose, potassium, sodium, urea nitrogen

- Urinalysis: glucose, protein

Any laboratory abnormality deemed clinically significant by the Investigator will be recorded as an AE.

8.5.4 Vital Signs

Vital sign data for ALT-103-201 subjects, including systolic blood pressure (mmHg), diastolic blood pressure (mmHg), temperature (C), and pulse rate (bpm), will be summarized descriptively for each dose group by time point for the observed value as well as for the change from baseline value. Any clinically significant abnormal vital sign value will be recorded as an AE.

8.5.5 ECG

ECG results for ALT-103-201 subjects will be summarized descriptively for each parameter and dose group by visit for the observed value as well as for the change from baseline value. In addition, a shift table will be provided comparing the baseline overall interpretation (normal, abnormal—not clinically significant, and abnormal—clinically significant) to the post-baseline value by visit.

8.5.6 Vector Shedding and Viral Culture

For the ALT-103-201 study, concentration of the Ad5 vector, as measured from nasopharyngeal swab samples to assess vaccine vector shedding by qPCR assay will be summarized descriptively for each dose group by visit. Negative results will be imputed to 1/2 LLOQ. These data will also be summarized by count and percentage of subjects with positive results by visit.

Viral culture data will be listed for ALT-103-201 subjects.

8.5.7 Other Safety Variables

Other safety variables, such as physical examination, drug and alcohol screen, pregnancy test, and serology (HIV, Hepatitis B and C) will be listed for ALT-103-201 only.

8.6 Immunogenicity Analysis

All immunogenicity analyses will be conducted on the PP Population. Analyses based on the ITT Population will be undertaken and presented only if >5% of subjects in any 1 dose group were excluded from the PP Population. Summaries and analysis will be completed by dose group and overall for subjects on an active NasoVAX dose.

The variables that will be analyzed, and the endpoints generated for each variable, are listed in Table 8-1:

Table 8-1. Immunogenicity Variables and Endpoints

Variable Name	GMT	GMR	SPR	SCR	Responder Rate	Geometric Mean SFUs	Compare to ALT-FLZ-401
A/California 2009 antibody level measured by HAI in serum	X	X	X	X			X
A/California 2009 antibody level measured by MN in serum	X	X			X		X
Cellular response to A/California 2009 peptides measured by enzyme-linked ELISpot in PBMCs					X	X	X
IgA antibody level measured by ELISA in nasopharyngeal swab	X	X					X
Antibody level measured by HAI in serum against the following nonrepresented strains: - A/Brisbane/59/2007 (H1 strain) - A/Saint-Petersburg/61/2015 (H1 strain) - A/New Jersey/76 (H1 strain) - A/Perth/16/2009 (H3 strain) - A/Vietnam/1203/2004XPR8 (H5 strain)	X	X			X		X
Antibody level measured by MN in serum against nonrepresented strains	X	X			X		X
Ad5 antibody levels in serum	X	X			X		

Note: Refer to Section 3 for descriptions of each endpoint.

Assay data will be tabulated by visit using the applicable endpoint(s) (e.g., GMT, GMR, or geometric mean SFUs) and their 95% CIs. Graphical representations of the longitudinal immune responses will also be given.

[figure not shown]
Analysis of covariance (ANCOVA) will be used in the analysis of the antibody levels at each post-baseline visit, with log-transformed antibody level as dependent variable, dose group as a factor, and baseline log-transformed level as a covariate. This model will be generated using SAS Proc Mixed with dose group in the CLASS statement and visit in the BY statement. Comparisons of post-baseline log-transformed antibody level will be conducted for each NasoVAX dose group against the placebo group and against the Fluzone group, if applicable. Least square (LS) means and 95% CI of the LS means of dose group, difference of LS means and 95% CI of the difference in LS means will be

obtained from the model via ESTIMATE statements. Back-transforming the difference of LS mean estimates and their 95% CIs to the original scale results in a ratio of the geometric means—these ratios will be reported in the summary.

Categorical data derived from the assay data (e.g., SPR, SCR, and responder rate) will be tabulated by counts and percentages per dose group, as well as the 95% Clopper-Pearson exact CI of the percentage. 95% CIs will also be presented to compare the response rate of each NasoVAX dose group to placebo and Fluzone (if applicable). CIs will be calculated in SAS PROC FREQ using the EXACT binomial-option for the individual dose groups and by the METHOD=SCORE riskdiff-option for the differences in dose groups [2]. In addition, comparisons of responders in each NasoVAX dose group against the placebo group and against the Fluzone group (if applicable) will be conducted using Fisher's exact test.

In addition, scatterplots of baseline Ad5 antibody levels along the x-axis will be presented with each of the following variables along the y-axis: HAI antibody titer at Day 29, ELISpot response at Day 8, and IgA response at Day 29 (one plot per dependent variable).

All data related to immunogenicity collection and analysis will be listed.

The logo for Summit Analytical features a stylized mountain range in the background, with a yellow sun rising behind the peaks. Below the graphic, the word "SUMMITANALYTICAL" is written in a light gray, sans-serif, all-caps font.

SUMMITANALYTICAL

9 References

1. Food and Drug Administration. Guidance for industry: Toxicity grading scale for healthy adult and adolescent volunteers enrolled in preventive vaccine clinical trials. Rockville, MD: U.S. Department of Health and Human Services; 2007b. Available at:
<http://www.fda.gov/downloads/BiologicsBloodVaccines/GuidanceComplianceRegulatoryInformation/Guidances/Vaccines/ucm091977.pdf>.
2. Newcombe RG. Interval estimation for the difference between independent proportions: comparison of eleven methods. *Statistics in Medicine* 1998 Apr 30;17(8):873-90

The logo for Summit Analytical features a stylized mountain range with a sun rising behind it. The sun is depicted as a yellow circle with rays, and the mountain peaks are represented by a series of curved lines in shades of yellow and grey. Below the graphic, the company name "SUMMIT ANALYTICAL" is written in a bold, sans-serif font, with "SUMMIT" in a darker grey and "ANALYTICAL" in a lighter grey.

SUMMIT ANALYTICAL

10 Appendices

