4.2. Inclusion and Exclusion Criteria

Subjects must satisfy all of the following criteria to be included in the study:

Inclusion Criteria

1. Men and women 18 to 50 years of age, inclusive
2. Good general health status, as determined by the Investigator
3. Adequate venous access for repeated phlebotomies
4. Screening laboratory results within institutional normal range or Grade 1 elevation if the Investigator documents clinical insignificance. Bilirubin may be Grade 2 if associated with normal alanine aminotransferase (ALT) and aspartate aminotransferase (AST) and the Investigator considers the result not to be clinically significant (e.g. vigorous exercise or Gilbert's syndrome)
5. Negative drug and alcohol screen at Screening and predose on Day 1
6. For women of child bearing potential (WOCBP), negative pregnancy test
7. Willingness to practice a highly effective method of contraception that may include, but is not limited to, abstinence, sex only with persons of the same sex, monogamous relationship with a postmenopausal partner, monogamous relationship with vasectomized partner, vasectomy, surgical sterilization (hysterectomy, or bilateral tubal ligation, salpingectomy, or oophorectomy), licensed hormonal methods, intrauterine device (IUD), or consistent use of a barrier method (e.g., condom, diaphragm) with spermicide for 28 days after the Fluzone Intramuscular Quadrivalent vaccine dose
8. Willingness to participate and comply with all aspects of the study through the entire study period, including nasal swabs and blood and urine samples
9. Provision of written informed consent

Exclusion Criteria:

1. Pregnant, possibly pregnant, or lactating women
2. Body mass index $> 35.0 \text{ kg/m}^2$
3. Positive results for HIV, hepatitis B virus, or hepatitis C virus at Screening
4. Asthma or other chronic lung disease that is greater than mild in severity. Specifically excluded are participants with any of the following events in the past year:
 - Daily symptoms
 - Daily use of short acting beta 2 agonists
 - Use of inhaled steroids or theophylline
 - Use of pulse systemic steroids
 - Emergency care or hospitalization related to asthma or other chronic lung disease
 - Systemic steroids for asthma exacerbation
5. History of diabetes mellitus (gestational diabetes is allowed if treatment was not required postpartum and serum glucose is currently in the normal range)
6. History of coronary artery disease, arrhythmia, or congestive heart failure

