
 To evaluate the mucosal immune response NasoVAX when administered by intranasal spray at a single dose of 1×10^9, 1×10^{10}, or 1×10^{11} vp 	
 Immunoglobulin A (IgA) antibody level measured by enzyme-linked immunosorbent assay (ELISA): 
 GMT GMR

 To evaluate the humoral immune response against nonrepresented influenza strains after NasoVAX administration 	
 Antibody level measured by HAI and MN in serum against each strain tested: 
 GMT GMR Responder rate: the number and percentage of subjects with 2-fold and 4-fold rise since baseline

 To evaluate the effect of predose adenovirus serotype 5 (Ad5) serum antibody levels on the immunogenicity of NasoVAX 	
 Predose Ad5 antibody GMT measured by MN in serum Day 29 GMR and responder rate from antibody level measured by HAI in serum

 To compare immunogenicity results to those obtained from banked samples from a previous study of licensed seasonal vaccine in a similar subject population (ALT-FLZ-401) 	
 Antibody level measured by HAI in serum: 
 GMT GMR SPR SCR Antibody level measured by MN in serum: 
 GMT Responder rate SFUs to hemagglutinin peptides measured by ELISpot in PBMCs: 
 Geometric mean SFUs Responder rate IgA antibody level measured by ELISA: 
 GMT GMR

4 Study Design

Study ALT-103-201 is a Phase 2a, randomized, double-blind, placebo-controlled trial to evaluate the safety, and immunogenicity of NasoVAX in healthy adults 18 to 49 years of age. Subjects will be screened within 28 days of randomization (Day 1). Approximately 60 subjects who meet all inclusion and no exclusion criteria and provide written informed consent will be enrolled into 3 sequential cohorts of 20 subjects each defined by the viral particle dose (1×10^9 , 1×10^{10} , and 1×10^{11} vp). Within each cohort and its sentinel group, subjects will be randomized in a 3:1 ratio to receive 1 intranasal dose of NasoVAX or placebo (Day 1) as shown in Table 4-1.

Table 4-1 NasoVax Study Design

Cohort	Dose (vp)	Number of Subjects	
		NasoVAX	Placebo
1	1×10^9	15	5
2	1×10^{10}	15	5

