All AEs and medications will be recorded from signing of the informed consent form to Day 29. Thereafter to the end of the study, only MAEs, NCIs, SAEs, immunosuppressive medications (see list in Appendix 3), and vaccines will be recorded. Samples for clinical laboratory tests (hematology, serum chemistry, urinalysis) will be collected at Screening and on Days 8 and 29. A complete physical examination and vital signs will be performed at Screening and predose on Day 1, and targeted and symptom-driven physical examinations will be performed and vital signs measured 2 hours postdose and on Days 4, 8, 15, and 29. An electrocardiogram (ECG) will be performed at Screening and on Day 29. If a subject experiences acute symptoms compatible with adenoviral infection within 28 days after the NasoVAX/placebo dose, a sample will be collected for viral culture as clinically indicated.

One interim analysis of humoral immunogenicity data and safety data (including summaries of AE, reactogenicity, concomitant medications and vaccines, vital signs, ECG, and laboratory data and listing of any viral culture results) will be conducted when all data through the Day 29 visit is available and monitored for all subjects.

A complete schedule of procedures and assessments for study ALT-103-201 is in Table 4-2.

ALT-FLZ-401, Extent and Durability of Immune Response Following Seasonal Influenza Vaccination in Healthy Volunteers, was an open label study designed to generate an immunogenicity sample set similar to that of ALT-103-201 in subjects receiving a licensed influenza vaccine based on the same H1 strain (A/California 2009). The seasonal vaccine H1 component changed at the time of the ALT-103-201 study to A/Michigan, so it was logistically much easier to conduct this study non-contemporaneously with the seasonal vaccine licensed for use in 2016-17. The same site, entry criteria and schedule of assessments for immunogenicity were followed. Twenty subjects were enrolled and samples from this study were frozen and stored and then shipped to blinded laboratory for immunogenicity testing in parallel to the samples from ALT-103-201. The schedule of events for ALT-FLZ-401 is in Table 4-3.

Table 4-2. ALT-103-201 TIME AND EVENTS SCHEDULE

Study Visit	Screening	Dosing Period							Follow-up Period	
		Day 1		Day 2 ^a	Day 4	Day 8	Day 15	Day 29	Day 91	Day 181
Window (days)	Day -28 to Day -1	Predose	Postdose		± 1	± 1	± 1	± 3	± 10	± 10
Informed consent	X									
Demographics	X									

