7.2 Randomization

ALT-103-201 Subjects will be enrolled into 3 sequential cohorts of 20 subjects each defined by the viral particle dose (1×10^9 , 1×10^{10} , or 1×10^{11} vp). Within each sentinel group and cohort, subjects will be randomized at a ratio of 3:1 ratio to receive 1 intranasal dose of NasoVAX or placebo on Day 1.

A sentinel cohort of 5 subjects from each cohort will be dosed. Dosing of the remainder of each cohort may proceed after the last sentinel subject completes Day 8 if no events meeting stopping criteria (Section 6.6 of the ALT-103-201 protocol) have occurred. The SRC, consisting of the Investigator, the Medical Monitor, and a Sponsor Representative, will review all AE, reactogenicity, and laboratory data through Day 8 for all subjects in each cohort before subjects are randomized to the next higher dose.

No randomization was required for the ALT-FLZ-401 study.

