7.4 Analysis of the Study

All statistical tests will be two-sided and a difference resulting in a p-value of less than or equal to 0.05 will be considered statistically significant. All p-values will be rounded to and displayed in four decimals. If a p-value less than 0.0001 occurs it will be shown in tables as <0.0001.

There will be no multiplicity adjustments.

To integrate the 2 studies for the immunogenicity tables, figures, and listings (TFL), subjects enrolled in ALT-FLZ-401 will be treated as an additional arm in the ALT-103-201 study. ALT-FLZ-401 subjects will be denoted as "Fluzone" subjects in the TFL, while ALT-103-201 will be denoted as "NasoVAX" if they are assigned to an active dose, or placebo if appropriate.

Descriptive summaries of variables will be provided where appropriate. Continuous variables will be presented for each dose group by geometric means and 95% confidence intervals (CIs) for the immunogenicity endpoints and by summary statistics (e.g., mean, and standard deviation [SD], median, minimum, and maximum) for other endpoints. Categorical variables will be presented by frequency distributions (including percentages and 95% CIs) for the immunogenicity endpoints and frequency counts and percentages for other endpoints. Expansion of descriptive table categories within each dose group may occur if such elaborations are thought to be useful.

All collected data will be presented in listings. Data not subject to analysis according to this plan will not appear in any tables or graphs but will be included in the data listings.

Post-hoc exploratory analyses not identified in this SAP may be performed to further examine the study data. These analyses will be clearly identified as such in the final clinical study report.

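### The NasoVAX-versus-Fluzone ANCOVA compares two separately recruited studies but adjusts only for baseline level; age and sex, collected in both, should be added for that contrast

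*SAP*

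**What the plan says.** SAP Section 8.6 specifies one ANCOVA per post-baseline visit on log antibody level, with "dose group as a factor, and baseline log-transformed level as a covariate". Each NasoVAX dose is compared "against the placebo group and against the Fluzone group, if applicable". Back-transforming the difference in LS means "results in a ratio of the geometric means", reported with a 95% CI.

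SAP Section 7.4 explains how Fluzone enters this model: "subjects enrolled in ALT-FLZ-401 will be treated as an additional arm in the ALT-103-201 study". SAP Section 7.2 adds: "No randomization was required for the ALT-FLZ-401 study". According to SAP Section 4, ALT-FLZ-401 was open-label and was not run at the same time as ALT-103-201.

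SAP Section 4 supports comparability with this sentence: "The same site, entry criteria and schedule of assessments for immunogenicity were followed". On age, the Protocol for ALT-FLZ-401 (Section 4.2) admits "Men and women 18 to 50 years of age, inclusive", whereas SAP Section 4 describes ALT-103-201 as a trial in "healthy adults 18 to 49 years of age".

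Age and sex are listed as baseline variables in SAP Section 6.2 and are summarised by group for both studies under Section 8.2. The SAP gives them no other role in immunogenicity: there is no covariate, matching, weighting or adjusted sensitivity analysis. SAP Section 3 lists the comparison with ALT-FLZ-401 among the exploratory objectives.

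**The concern.** One model serves two contrasts of different standing. Against placebo, randomisation within cohorts protects the NasoVAX estimate, and leaving out age and sex is not a confounding problem. Against Fluzone there is no such protection. Shared entry criteria limit the range of ages admitted, but they do not equalise the mean age or the share of women between two groups recruited at different times. Baseline level removes only the part of an age or sex difference that acts through baseline level.

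If the two studies drew systematically different mixes of subjects, and age or sex affects response beyond baseline level, the difference shifts the GMT ratio. The interval is then centred in the wrong place, and its width does not reflect the shift. The comparison with a licensed vaccine extends across HAI, MN, ELISpot and IgA, with two-sided tests at 0.05 and no multiplicity adjustment (SAP Section 7.4). A reader could take a shifted ratio as a vaccine effect.

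**Working it through.** The plan states no power, effect size or SD for this comparison, so there is no figure of its own to reproduce.

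**Inputs from the documents.** 15 subjects per NasoVAX dose (SAP Table 4-1), 20 Fluzone subjects (SAP Sections 4 and 7.1), and 80 in total (45 NasoVAX, 15 pooled placebo, 20 Fluzone). Per-protocol numbers may be smaller.

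**Assumptions, because the documents give no values.** Age effect 0.02 to 0.04 log2 per year and sex effect 0.3 to 0.5 log2, both remaining after baseline adjustment; age SD 9 years; about half women; residual SD 1.0 to 1.5 log2; age and sex gaps acting in the same direction.

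**Step 1: chance imbalance.** sqrt(1/15 + 1/20) = 0.342. With age SD 8 to 10 years, the SE of the mean-age gap is 2.7 to 3.4 years, so 95% limits are about ±5.4 to ±6.7 years. The SE of the gap in the share of women is 0.5 × 0.342 = 0.171, with limits of about ±33 points. These gaps look large, but if both groups come from one population the variation sits in the residual variance, which sets the CI width. Simulating 15 versus 20 subjects from one population, with a baseline-only ANCOVA and the effects above, gives coverage of 94.9% to 95.1%. Chance imbalance is covered.

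**Step 2: the documented systematic difference.** With ages spread evenly, mean age is (18 + 50)/2 = 34.0 against (18 + 49)/2 = 33.5, a gap of 0.5 year. At the steeper slope the factor is 2^(0.04 × 0.5) = 1.014, which is trivial.

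**Step 3: a larger systematic difference (illustration).** Log2 bias b = slope × age gap + sex effect × gap in share, and the factor is 2^b. Approximate coverage is Φ(1.96 − d) − Φ(−1.96 − d), with d = b/SE and SE = 0.342 × sqrt(residual SD² + (slope × 9)² + 0.25 × sex effect²).

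| Effects (age, sex) | Gap | b | Factor | Coverage, SD 1.0 | Coverage, SD 1.5 |
|---|---|---|---|---|---|
| 0.02, 0.3 | 3 y, 17 points | 0.06 + 0.051 = 0.111 | 1.08 | 93.8% | 94.5% |
| 0.04, 0.5 | 3 y, 17 points | 0.12 + 0.085 = 0.205 | 1.15 | 91.5% | 93.3% |
| 0.02, 0.3 | 6 y, 34 points | 0.12 + 0.102 = 0.222 | 1.17 | 90.3% | 92.9% |
| 0.04, 0.5 | 6 y, 34 points | 0.24 + 0.17 = 0.410 | 1.33 | 80.4% | 88.0% |

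For the last row at SD 1.0: SE = 0.342 × sqrt(1 + 0.130 + 0.0625) = 0.373 and d = 0.410/0.373 = 1.10. Simulation of the same settings gives about 81% to 94% for the baseline-only model and about 95% once age and sex are added.

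**Step 4: scale.** The 95% CI factor on the ratio is exp(t × SD_ln × 0.342), or 1.61 at ln-SD 0.7 and 1.98 at ln-SD 1.0. Residual SDs of 1.0 and 1.5 log2 are 0.69 and 1.04 on the ln scale, so these are the relevant values. The illustrated bias is smaller than the sampling error but not negligible.

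**Step 5: cost in precision.** Residual degrees of freedom go from 80 − 6 = 74 to 72. At ln-SD 1.0 the CI factor moves from 1.975 to 1.976. If the groups really differ in age or sex the adjusted interval also widens, because the covariates then overlap with group.

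**The case against.** The strongest objection is that an imbalance between 15 and 20 subjects is ordinary sampling error, which the interval already reflects. This stands. A reader might infer from the chance gaps in Step 1 that the ratio is biased in a way the CI misses; the coverage of about 95% shows otherwise. The same chance gaps arise between NasoVAX and placebo, where no change is needed.

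A second objection is that the only systematic difference in the documents is an upper age limit of 50 against 49. This also stands. A reader might take that mismatch as evidence of material bias, but at a factor of about 1.01 it is a wording error and no more. The documents give only the age range for ALT-103-201, so its other criteria cannot be compared here.

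Third, the design has real safeguards. SAP Section 4 reports the same site, and Section 7.4.2 has samples from both studies pooled and assayed together by a laboratory blind to study. The age and sex tables will show any imbalance, and labelled post-hoc analyses are allowed. These points lower the risk, but the assay safeguards act on measurement, not on who was enrolled. An adjustment chosen after the imbalance is seen is also weaker than one prespecified.

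Fourth, age and sex terms cannot make the contrast unconfounded, because Fluzone is fully aliased with its study and season. This is correct, and it limits what the change can deliver.

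**Conclusion.** The point holds as a risk in an exploratory comparison. The Fluzone contrast is non-randomised, crosses two studies run at different times, and adjusts only for baseline level although age and sex are available in both.

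The documents do not support saying that the ratio is biased. They give no age or sex distribution by group, no effect of either on titer and no residual SD, so size and direction are unknown. There is no bias if recruitment was balanced, or if age and sex have no effect beyond baseline level. The factor of about 1.08 to 1.33 and coverage of about 81% to 94% depend entirely on the assumed effects, the assumed systematic gaps of 3 to 6 years and 17 to 34 points, and both gaps acting in the same direction.

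The change is worth making because the data already exist and the loss of degrees of freedom is negligible. The exploratory status and the safeguards keep it at moderate importance.

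**What to change.** In SAP Section 8.6, for the Fluzone contrasts only, prespecify an ANCOVA with age (continuous) and sex added to dose group and baseline log level, and report the baseline-only model alongside it. Leave the randomised NasoVAX-versus-placebo model unchanged. State which groups enter the adjusted model: if placebo subjects help to estimate a common age or sex slope, that slope may not suit the vaccinated groups.

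Label every Fluzone comparison as non-randomised, in tables and text, because study and season remain inseparable from vaccine after adjustment. In SAP Section 4, correct the sentence on entry criteria to state ages 18 to 50 in ALT-FLZ-401 and 18 to 49 in ALT-103-201.

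The cost is a second model per visit with its own LS means, which the tables must keep apart from the first set, and two residual degrees of freedom. No new data are needed.
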